#### 5.3. Inclusion criteria:

- Neonates of all gestational ages admitted to Foothills Medical Centre and Alberta Children's Hospital NICU
- PICC line insertion planned as part of NICU care
- Venous access available in both upper (above umbilicus) and lower body

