#### 5.5. Randomization:

Eligible infants will be randomly assigned for upper extremity or lower extremity PICC insertion using an allocation ratio of 1:1. We will use blocked randomization of varying block sizes in multiples of two. The investigators will be blinded to the block sizes; but the block sizes will ensure appropriate balance between both arms. Infants will be stratified into two groups based on the gestational age ( $\leq 32$  weeks,  $>32$  weeks). Randomization will be performed using computer generated software once eligibility is confirmed and informed consent is obtained. A unique patient identification number and the randomisation sequence will be generated.

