#### 5.6. Interventions:

PICC insertion attempts will be made by certified health care providers including transport nurses, nurse practitioners and physicians using standard clinical practice guidelines. A maximum of two attempts will be allowed in the designated region, following which further attempts will be considered in the non-designated region if the inserter is confident of success. Number of attempts at insertion and sites of attempts will be recorded as per unit protocol. After the catheter is inserted, catheter tip position will be confirmed by radiograph with the limbs in standard position as per unit protocol, and repeat radiographs will be taken if there is a manipulation. As per unit protocol, the catheter inserter will record the details of the procedure, the type of catheter used, and position of catheter following radiographic confirmation in the progress note of each infant's medical chart. Similarly, the bedside nurse also documents this information in the nursing chart/Metavision. In addition, the inserter will fill out a one-page PICC line tracking sheet for all the lines which includes details such as the indication, date of insertion, site of insertion, catheter tip position, and any complications during insertion. Once the

PICC is removed, the bedside nurse will complete the PICC tracking sheet, filling in the date and the reason for removal of the line.

The clinical goal is to place the catheter tip in the superior vena cava or inferior vena cava, but outside the right atrium. A catheter tip lying beyond the medial end of the clavicle and up to 1 cm at the junction of right atrium and superior vena cava is considered optimal for upper extremity. PICCs with the catheter tip located in the inferior vena cava below the diaphragm are considered optimal for lower extremity PICCs. Heparin will be infused in all PICCs as per standard unit policy. All catheters will be removed either after completion of intravenous therapy or earlier if they develop complications. In all babies an ultrasound will be performed within 72 hours of PICC line removal by neonatologists trained to perform point of care ultrasound, looking for the presence of an occlusive thrombus. If one is detected, consultation to radiology and hematology will be requested as per unit protocol.

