## 7.2. Statistical methods:

Data will be analyzed using intention-to-treat analysis. Baseline demographics of the study population will be described using descriptive statistics. Data will be checked for normality. Categorical variables will be presented as counts and percentages and continuous variables as mean and standard deviation or median and inter-quartile range if data are not normally distributed. Primary outcome, which is the presence of any complication, necessitating PICC removal, is a binary outcome where we will use chi-squared test or Fisher exact test. Event rates, relative risk and 95% confidence intervals will be reported for primary outcome. Secondary outcome, which is the time from PICC insertion to development of complication, is a continuous outcome for which two sided independent samples t-test or Mann-Whitney U test, depending on if the data is normally distributed or not. Standard deviation and 95% confidence interval will be reported for continuous outcomes. We will also calculate time to complication post insertion as median time. We will also do multivariate logistic regression analysis to examine the association of PICC site and complication rate after adjusting for gestational age, day of PICC insertion and illness severity score. P-value <0.05 will be taken as significant. Stata 15 will be used for the analysis.

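### The additional adjusted model in 7.2 uses day of PICC insertion, which is fixed after randomisation and undefined for an infant who gets no PICC; a baseline covariate and the allocated arm should be used instead

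*Combined protocol and SAP*

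**What the plan says.** The order of events is clear. An infant is eligible with "PICC line insertion planned as part of NICU care" (5.3), and "Randomization will be performed using computer generated software once eligibility is confirmed and informed consent is obtained" (5.5). Insertion comes afterwards: "A maximum of two attempts will be allowed in the designated region", after which "further attempts will be considered in the non-designated region if the inserter is confident of success" (5.6).

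Section 7.2 states "Data will be analyzed using intention-to-treat analysis". The primary outcome "is a binary outcome where we will use chi-squared test or Fisher exact test", reported with a relative risk and its confidence interval. The section then adds: "We will also do multivariate logistic regression analysis to examine the association of PICC site and complication rate". This model is to be fitted "after adjusting for gestational age, day of PICC insertion and illness severity score".

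The plan does not define day of PICC insertion (calendar day, postnatal day, or days from randomisation). It does not say when the severity score is taken, whether PICC site means the allocated or the actual site, what happens to records with a missing covariate, or how an infant who never receives a PICC is counted.

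**The concern.** A covariate in an intention-to-treat model should be fixed before allocation. Day of insertion is not, on any reading of the term. If a first-choice site is harder to cannulate, the two permitted attempts and a possible move to the other region can push insertion later in that arm. The covariate may then carry part of the consequence of allocation.

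It is also undefined for an infant with no PICC. Section 5.6 allows that outcome, because attempts in the other region are conditional on the inserter's judgement. Logistic regression software omits records with a missing covariate by default, so these infants would leave the model without any stated decision to exclude them.

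What is at stake is how the adjusted result is read. If it differs from the unadjusted one, a reader will credit adjustment for prognosis, when part of the difference may come only from a change in the population analysed.

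**Working it through.** **The plan's own figures.** No figure in the plan bears directly on this point, since it gives no no-placement rate. The numbers used here are 320 infants and 1:1 allocation (7.1, 5.5), so 160 per arm, and the 30% complication rate (7.1). The stated 153 per arm was checked and is not reproduced by a two-sided two-proportion formula: for 30% vs 20%, n = [1.96√(2×0.25×0.75) + 0.842√(0.3×0.7 + 0.2×0.8)]² / 0.10² gives 294 per arm. That is a separate matter, and nothing below depends on it.

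**1. Infants lost.** Let f be the share with no PICC in each arm (assumed). Infants lost = 160 × (f₁ + f₂).

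| Assumed f, arm 1 / arm 2 | Lost of 320 |
|---|---|
| 0% / 0% | 0 |
| 1% / 1% | 3.2 |
| 2% / 2% | 6.4 |
| 5% / 5% | 16 |
| 2% / 10% | 19.2 |
| 5% / 10% | 24 |
| 10% / 10% | 32 |

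At the top of the range, 144 per arm remain. The standard error grows by about √(160/144) = 1.054, or 5%. Power of an unadjusted 30% vs 20% comparison falls from 54.2% at 160 per arm to 50.0% at 144.

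**2. Change in what is estimated.** Assume 30% events among infants with a PICC in both arms, and count infants with no PICC as event-free (a literal reading of 6.1, where the event is a complication that leads to PICC removal).

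- Unequal loss, 2% vs 10%: the rates over all randomised infants are 0.30 × 0.98 = 29.4% and 0.30 × 0.90 = 27.0%. RR = 27.0/29.4 = 0.92; OR = (0.270/0.730)/(0.294/0.706) = 0.89. With these infants dropped, both ratios are 1.00.
- Equal loss, 5% vs 5%: 28.5% in both arms, and ratios of 1.00 with or without them.

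The two analyses therefore diverge in this example only if no-placement differs by arm.

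**3. Bias from conditioning.** This was simulated with 400,000 infants per scenario, no true site effect, and every infant receiving a PICC. Day of insertion was age at randomisation plus a delay that depended on an unmeasured severity variable and, in some scenarios, on arm. All these inputs are assumed.

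| Arm difference in delay | Log-odds effect of severity per SD | OR adjusted for day of insertion | OR adjusted for age at randomisation |
|---|---|---|---|
| 0 days | 0.5 | 0.995 | 0.995 |
| 0 days | 1.0 | 0.996 | 0.996 |
| 1 day | 1.0 | 0.983 | 0.996 |
| 2 days | 0.5 | 0.984 | 0.997 |
| 2 days | 1.0 | 0.972 | 1.000 |

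Simulation error in each OR is about 0.007. With equal delay the choice of covariate makes no difference. A visible shift needs both a delay that differs by arm and a severity effect shared with the outcome, and even then it is about 0.03.

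**The case against.** The strongest reply is that the problem may never arise. Section 5.3 requires venous access in both upper and lower body, and 5.6 lets either arm move to the other region after two attempts. Ending with no PICC would then usually mean that both regions failed or the second was not tried, whichever was allocated first. If every infant receives a PICC, this covariate drops nobody. If insertion follows randomisation closely, day of insertion is nearly a baseline value.

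Much of that stands, and it rules out three stronger readings.

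- *That the model will drop randomised infants, and more from one arm.* The documents give no failed-insertion rate, no difference by arm and no complete-case rule. The loss is something the plan permits, not something it predicts.
- *That conditioning on this covariate materially distorts the site effect.* Nothing in the documents says that delay differs by site, or that a failed attempt moves insertion to another day. The simulated shift was small under deliberately unfavourable assumptions.
- *That the trial's main result is affected.* The primary test is unadjusted and does not use the covariate; the logistic model is additional.

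The reply does not remove the structural point. The covariate is set after allocation and can be undefined, and the plan's own intention-to-treat statement has no exception for this model.

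**Conclusion.** The point holds as a minor inconsistency confined to the additional adjusted model. Day of PICC insertion is fixed after randomisation, open to influence by the allocated site, and has no value for an infant with no PICC. In an ordinary fit such infants would be left out, contrary to intention to treat.

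The range of loss rests on the assumed 0 to 10%, which includes zero and equal loss. The OR of 0.89 vs 1.00 further requires unequal no-placement of 2% vs 10% and the event-free convention.

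A reader might also infer that replacing this one covariate would bring every randomised infant into the model. It would not. If PICC site means the actual site, an infant with no PICC has no exposure value either, and the model is not intention to treat whichever covariates it contains. The exposure therefore has to be fixed together with the covariate.

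**What to change.** In 7.2, for the adjusted logistic model:

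- replace day of PICC insertion with postnatal age at randomisation;
- use an illness severity score taken at or before randomisation, and say when it is taken;
- enter the allocated arm, not the actual PICC site, as the exposure;
- count infants who receive no PICC in the same way as in the primary intention-to-treat analysis. The plan does not yet state that rule, so write it once and apply it to both analyses.

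The cost is a few lines of text. Age at randomisation needs only the dates of birth and randomisation, which are available for every infant. The one item to confirm is that the intended severity score can be obtained by the time of randomisation, since the plan does not give its timing. Sample size and the primary test are unchanged.

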## 8. Trial administration:

**8.1. Clinical Site:** This multicentre study will be conducted at the Neonatal Intensive Care Unit, in Foothills Medical Center and Alberta Children's Hospital NICU, Calgary, Canada

**8.2. Steering Committee and Local Operations Group:** The steering committee will consist of two neonatologists, two transport nurses, one Clinical Trials Coordinator and one nurse clinician. Along with these, there will be a study physician committed to the trial and a research assistant responsible for the daily conduct of the trial including recruitment, informed consent, administration of intervention, data collection, and in-servicing of relevant NICU staff.

**8.3. Data Safety Monitoring Board (DSMB):** This committee will be made up of two separate neonatologists, a statistician, and a unit manager, who will be blinded to the two groups. They will function independently from the study investigators. Once half the intended recruitment is reached, an interim analysis of clinical outcome data for efficacy and data analysis for expected and unexpected adverse events will be done. The DSMB will recommend termination of the trial for statistically significant ( $p < 0.001$ ) differences between the intervention groups with respect to PICC related complications, mortality, or serious unexpected adverse events. Results of the interim analysis will not be disclosed to investigators or study participants but will be published along with the DSMB's recommendations upon completion of the trial.

**8.4. Data Collection:** All data collection will be done with the help of a research assistant, supervised by a physician who is committed to the study. The study physician will check the data collection forms for completeness of data and fill each form separately. The study data will be collated and entered into the study database for analysis. Completed data collection forms and all the reporting forms will be securely locked in a closed cabinet in the study Principal Investigator's office at FMC.

**8.5. Study Monitoring:** The specific committee will ensure that all study procedures are in compliance with good clinical practice. It is imperative that the study proposal and all the amendments will be approved by the local Research Ethics Board.

**8.6. Data Quality Assurance:** Baseline infant demographics, details of PICC insertion and maintenance will be obtained from patient chart and electronic medical record. X-ray for PICC position and ultrasound reports and images to screen for thrombus will be available in the

IMPAX. Details of infusing solution through the PICC line as well as laboratory parameters will be available in the electronic medical record.

**8.7. Regulatory Approval:** All the interventions used for the conduct of the study has been approved by Health Canada, hence no special permissions are required.

**8.8. Subject Confidentiality:** Appropriate measures will be taken to maintain subject confidentiality. Although hospital database will have personal identifiers, only the random ID will be available in the research database. Privacy of electronic records will be maintained in the secure hospital server. Since the intervention cannot be blinded, the most responsible physician and the research team will know about any adverse event which occurs.

**8.9. Retention of Records:** As per Health Canada and local Research Ethics Board, paper records will be maintained for 5 years and electronic records for 7 years before destroying.

**8.10. Documentation of Protocol Deviations:** Research staff will be instructed to report all protocol violations in a particular reporting form created for the purpose.

**9. Ethical Considerations:**

This study will be conducted in accordance with the Good Clinical Practice guidelines and local Research Ethics Board requirements. Parents will act as surrogate decision makers for the patient.

**10. Feasibility and limitations:**

Major limitation of the study is the large sample size. We expect around 320 babies to be enrolled to see an effect. In our retrospective study, there were around 900 first time PICCs over a period of 5 years from 2006- 2010, which gives an average of 180-200 PICCs per year. Accordingly, it will take about 1.5-2 years to finish the trial.

**11. Impact of the study:**

The results of this trial will help to figure out if there is an association with increased complication rates when PICC lines are inserted through upper or lower extremities. If there is a significant difference detected, it will definitely guide the inserter to select the site with fewer complications, especially in a neonate with first time PICC insertion, rather than base the choice of site of insertion on personal preference and venous accessibility.

